14.7.3 Publication

The results from this study may be submitted for publication and/or presented during conferences at the discretion of the Sponsor.

14.8 Archiving

The Principal Investigator is responsible for maintaining essential documents, (as defined in ICH E6 GCP, Section 8) for 10 years after finalization of the CSR. This includes any original source documents related to the study, the Subject Identification List (providing the sole link between named subject source records and anonymous eCRF data), the original signed ICFs and detailed records of disposition of IP.

It is the responsibility of the Sponsor to inform the Investigator/institution as to when these documents no longer need to be retained.

The Sponsor will archive the TMF in accordance with ICH E6 GCP, Section 8 and applicable regulatory requirements.

The data from the eCRFs will be sent to the Sponsor and a copy will be sent to the clinic and filed in the Investigator Study File for archiving for 10 years after finalization of the CSR.

The completed eCRFs are the sole property of the Sponsor and should not be made available in any form to third parties, except for authorized representatives of appropriate Health/Regulatory Authorities, without written permission from the Sponsor.

15 DATA MANAGEMENT

The data management routines include procedures for handling of the eCRF, database set-up and management, data entry and verification, data validation, QC of the database, and documentation of the performed activities including information of discrepancies in the process. The database, data entry screens, and program will be designed in accordance with the CSP.

Data validation/data cleaning procedures are designed to assure validity and accuracy of clinical data. These procedures consist of computerized online edit checks identifying e.g. data values that are outside the allowed range and SAS-programmed batch checks on data exports. All study-specific and standard data validation programming will be tested in a separate testing environment prior to use on production data.

Detailed information on data management will be described in a study-specific Data Management Plan (DMP).

15.1 The web-based eCRF

Clinical data will be entered into a 21 CFR Part 11-compliant eCRF (Viedoc™) provided by Viedoc Technologies AB. The eCRF includes password protection and internal quality checks, such as automatic range checks, to identify data that appear inconsistent, incomplete, or inaccurate. Clinical data will be entered directly from the source documents or at bedside (if the eCRF data constitutes source data). Source data are to be defined at the site before inclusion of the first subject (Section 14.3).

Authorized site personnel designated by the Investigator will complete data collection. Appropriate training and security measures will be completed with the Investigator and all authorized trial site personnel prior to the trial being initiated and any data being entered into the system for any study subject.

15.2 The entering of data into the eCRF

All entries, corrections, and alterations are to be made by the Investigator or designee. Neither the Monitor nor any other study team member besides site staff can enter data in the eCRF. All data should be entered in English. The eCRFs should be completed as soon as possible during or after the subject's visit. To avoid inter-observer variability, every effort should be made to ensure that preferably the same individual who made the initial baseline determinations completes all corresponding follow-up evaluations. The Investigator must verify that all data entries in the eCRFs are accurate and correct. If some assessments are not done, or if certain information is not available, not applicable, or unknown, the Investigator or assigned clinical staff should record such information in the eCRF. The Investigator will be required to electronically sign off the clinical data. This will be performed by means of the Investigator's unique User ID and password; date and time stamps will be added automatically at time of electronic signature.

15.3 The query process

The Monitor will review the eCRFs and evaluate them for completeness and consistency. Data in the eCRF will be compared with the respective source documents to ensure that there are no discrepancies for critical data as described in the RBM plan. All entries, corrections, and alterations are to be made by the Investigator or designee. Neither the Monitor nor any other study team member besides site staff can enter data in the eCRF.

If corrections are needed, queries will be raised within the eCRF, either as a result of built-in edit checks or manually raised by the monitor. An appropriate member of the site staff will answer the queries in the eCRF either by correcting the data or by entering a response to the query. The monitor will either approve the answer/correction or re-issue the query.

15.4 Audit trail

All entries in the eCRF will be fully recorded in a protected audit trail. Once clinical data have been saved, corrections to the data fields will be audit trailed, meaning that the reason for change, the name of the person who made the change, together with time and date will be logged.

15.5 External data

External data consists of data that are not recorded in the eCRF. Data may be received in electronic format or as a paper printout. Key variables are defined in order to uniquely identify each sample record. File and data formats are agreed with the external data provider.

15.6 Medical coding

Medical coding will be performed by trained personnel at CTC. AEs and medical/surgical history verbatim terms will be coded using the Medical Dictionary of Regulatory Activities (MedDRA; latest version available at start of coding). Prior and concomitant medications will be coded according to the World Health Organisation (WHO) Anatomic Therapeutic Chemical (ATC) classification system. All coding will be approved by Sponsor prior to database lock.

15.7 Database lock

When all data have been entered and discrepancies solved, clean file will be declared, the database will be locked and the data will be analyzed.

16 STATISTICAL METHODS AND DETERMINATION OF SAMPLE SIZE

The principal features of the statistical analysis to be performed are described in this section. A more technical and detailed elaboration of the principal features will be presented in a separate Statistical Analysis Plan (SAP), which will be signed and approved prior to database lock.

Analyses of the primary and secondary endpoints will be performed by CTC.

16.1 General

Continuous data will be presented in terms of evaluable and missing observations, arithmetic mean, standard deviation (SD), median, minimum and maximum value.

Categorical data will be presented as counts and percentages. When applicable, summary data will be presented by treatment, and by assessment time. Individual subject data will be listed by subject number, treatment, and, where applicable, by assessment time.

All descriptive summaries and statistical analyses will be performed using SAS Version 9.4 or later (SAS Institute, Inc., Cary, NC).

All pairwise testing will use a significance level of 5%.

No imputation of missing data will be performed.

16.2 Determination of sample size

The main hypothesis is to show that the fraction of extracted nicotine in ZYN Wintergreen is equivalent to that of Zyn Smooth.

Former studies (SM-17-03 and SM 18-01) has shown that the fraction of extracted nicotine has a mean CV of 31%, using a power of 80% and a 90% confidence interval (0.8-1.25) for the ratio will give a sample size of 33 subjects needed to show equivalence between the ZYN Wintergreen and ZYN Smooth (using Proc Power in SAS). In order for a small number of dropout will 36 subjects be included.

16.2.1 Full analysis set

The Full Analysis Set (FAS) will consist of all subjects who have been randomized and received at least one dose of IP and who has at least one post-baseline assessment of efficacy data. This population will be used as the Safety analysis set.

16.2.2 *Per protocol set*

The Per Protocol Set (PPS) will consist of all subjects who have been randomized and completed the study without any major protocol deviations that are judged to compromise the analysis of the data. All protocol violations will be judged as major or minor prior to database lock.

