7 STUDY OBJECTIVES AND ENDPOINTS

Objectives and endpoints are summarized in Table 7-1.

Table 7-1 Objectives and endpoints

Primary objective	Endpoint	Assessment(s)
The primary objective of the study is to show equivalence of the estimated in vivo extracted fraction of nicotine between ZYN Wintergreen (1) and ZYN Smooth after administration of one single dose.	Estimated in vivo extracted fraction of nicotine.	Collection of used snus pouches
Secondary objective	Endpoint	Assessment(s)
To compare the estimated in vivo extracted amount and fraction of nicotine from each product*.	Estimated in vivo extracted amount and fraction of nicotine.	Collection of used snus pouches
To evaluate the estimated in vivo extracted amount and fraction of flavor compounds*.	Estimated in vivo extracted amount and fraction of flavor compounds.	Collection of used snus pouches
To evaluate safety and tolerability of ZYN products.	Frequency, intensity and seriousness of adverse events (AEs).	Collection of AEs

*See section 9.9 for included products

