9.8 Subject withdrawal

9.8.1 *General withdrawal criteria*

Subjects are free to discontinue their participation in the study at any time and for whatever reason without affecting their right to an appropriate follow-up investigation or their future care. If possible, the reason for withdrawal of consent should be documented.

Subjects may be discontinued from the study at any time at the discretion of the Investigator.

Reasons for discontinuation include:

- Subject decision
- Severe non-compliance to study protocol procedures, as judged by the Investigator and/or Sponsor
- Subject is lost to follow-up.
- Significant AEs posing a risk for the subject, as judged by the Investigator and/or Sponsor
- Pregnancy
- Death

9.8.2 *Procedures for discontinuation of a subject from the study*

A subject who prematurely discontinues participation in the study will always be asked about the reason(s) for discontinuation and the presence of any AEs. If a subject withdraws consent, the Investigator must ask the subject if he/she is willing, as soon as possible, to be assessed according to the procedures scheduled for the end-of-study visit. Any ongoing AEs will be followed as described in Section 11.4.11.

The primary reason for discontinuation/early withdrawal must be specified in the eCRF and final IP accountability must be performed.

9.8.3 *Subject replacement*

Subjects who are prematurely withdrawn from the study may be replaced at the Sponsor’s discretion after consultation with the Investigator.

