11.3 Assessments related to primary and secondary endpoints

11.3.1 *Nicotine and flavor compounds extraction from pouches*

Used pouches will be collected after 60 minutes (+/- 1 minute) of use for the determination of residual nicotine and flavor compounds in the IPs.

All the collected pouches will be frozen immediately at -20°C. Pouches for extraction of nicotine and flavor compounds will be analyzed by Swedish Match and Eurofins Food & Feed Testing Sweden.

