11.4 Adverse events

In this study, the IP is a nicotine product and not an investigational medicinal product. However, the procedures for monitoring, collecting, and reporting of AEs will be the same as for an investigational medicinal product, as far as possible. The Principal Investigator is

responsible for ensuring that all medical staff involved in the study are familiar with the content of this section and the content of the CTC standard operating procedures (SOPs) regarding emergencies and Phase I studies.

11.4.1 *Definition of adverse event*

An AE is defined as any untoward medical occurrence in a subject administered an IP and which does not necessarily have a causal relationship with this IP. An AE can therefore be any unfavorable and unintended sign, symptom, or disease temporally associated with the use of an IP, whether or not considered related to the IP.

11.4.2 *Definition of serious adverse event*

An SAE is any AE which:

- results in death
- is life-threatening (this refers to a reaction in which the subject was at risk of death at the time of the reaction; it does not refer to a reaction that hypothetically might have led to death if the reaction was more severe)
- requires in-patient hospitalization or prolongation of existing hospitalization
- results in persistent or significant disability/incapacity
- is a congenital anomaly/birth defect
- is an important medical event (IME) (this refers to a reaction that may not be immediately life-threatening or result in death or hospitalization, but may jeopardize the subject or may require intervention to prevent any of the other outcomes defined above)

Examples of IMEs are intensive treatment in an emergency room for allergic bronchospasm or blood dyscrasias, convulsions that do not result in hospitalization, development of drug dependency, and drug abuse.

Planned hospitalizations or surgical interventions for a condition that existed before the subject signed the ICF and that did not change in intensity are not SAEs.

If there is any doubt as to whether an AE meets the definition of an SAE, a conservative viewpoint must be taken, and the AE must be reported as an SAE.

11.4.3 *Time period and frequency for collecting adverse events*

All AEs (including SAEs) will be collected from the start of IP use until the end-of-study visit.

Any AE with start date on the day of the first IP use must be recorded with start time.

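### The Safety analysis set is made identical to the FAS, so a dosed subject with no pouch result from any dose falls outside it, even if an adverse event is the reason

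*Protocol*

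**What the plan says.** Section 16.2.1 admits to the FAS randomized subjects who have had at least one dose, and adds a further condition: "who has at least one post-baseline assessment of efficacy data. This population will be used as the Safety analysis set". Section 16.2.2 defines only the per-protocol set, so this is the protocol's only safety population.

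Safety is a stated secondary objective in Table 7-1: "To evaluate safety and tolerability of ZYN products". Its endpoint is the frequency, intensity and seriousness of AEs. Section 11.4.1 defines events by exposure: "An AE is defined as any untoward medical occurrence in a subject administered an IP". Section 11.4.3 does the same for collection: "All AEs (including SAEs) will be collected from the start of IP use until the end-of-study visit".

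The protocol does not define efficacy data. Apart from AEs, the only endpoints are extraction results from pouches, for which Section 11.3.1 says: "Used pouches will be collected after 60 minutes (+/- 1 minute) of use". Section 16.1 rules out imputation.

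Section 16.5.3 plans an overview of every AE by system organ class and preferred term, plus a full listing, and names no analysis set for either.

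**The concern.** A safety population is normally defined by exposure, because a condition that depends on later data can be affected by the outcome being measured. Here the added condition is a pouch result, and planned collection comes only after an hour of use. Section 9.8.1 allows a subject to leave at any time and lists this among the reasons for discontinuation: "Significant AEs posing a risk for the subject, as judged by the Investigator and/or Sponsor". A subject who reacts to the first pouch, stops, and leaves nothing that can be assayed would have been exposed, would have an AE on record, and would not belong to the Safety set. The event that should be counted would be the reason the subject is not counted.

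At stake are the descriptive AE incidences that answer the secondary safety objective. An event seen only in such a subject would be missing from a table built on the Safety set, and its denominator would be short by one.

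**Working it through.** The protocol gives no figure for this point, so the check is one of logic first and of possible size second.

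**Set membership.** Take a subject who is randomized, receives one dose, has an AE and yields no pouch result from any dose.

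| Condition or rule | Where | Met? |
|---|---|---|
| Randomized | 16.2.1 | yes |
| At least one dose | 16.2.1 | yes |
| At least one efficacy assessment after baseline | 16.2.1 | no |
| In the FAS, hence in the Safety set | 16.2.1 | no |
| Event meets the AE definition and is collected | 11.4.1, 11.4.3 | yes |
| Event falls within the overview and listing | 16.5.3 | yes as worded; no set named |

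Sections 11.4 and 16.5.3 count this subject; Section 16.2.1 does not.

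**Who can be affected.** One result from any of the nine doses keeps a subject in the set. Exclusion needs failure at the first pouch and at every later one, which in practice means stopping at or soon after the first dose, or having every pouch lost or unassayable. Under Section 9.9 each visit starts with treatment A or B, so a loss at the very first dose concerns Wintergreen (1) or Smooth.

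**Size.** Let n be the number dosed (36 planned, Section 9.3) and k the number dosed without any pouch result. The protocol gives no k; 1 to 3 is an assumed range.

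| k | Safety set as written, 36 − k | Share of dosed subjects lost, k/36 |
|---|---|---|
| 1 | 35 | 2.8% |
| 2 | 34 | 5.6% |
| 3 | 33 | 8.3% |

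Suppose x subjects inside the set have a given event and all k excluded subjects have it too. The incidence among all dosed is (x + k)/n, and the Safety set shows x/(n − k). The shortfall is

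(x + k)/n − x/(n − k) = k(n − k − x) / [n(n − k)],

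which is largest at x = 0, where it equals k/n. The percentages in the last column are therefore upper limits on the understatement.

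With k = 1 and x = 0, the table would show 0/35, with an exact 95% upper limit of 1 − 0.025^(1/35) = 10.0%. Among all dosed subjects it is 1/36 = 2.8%, with an exact 95% interval of 0.1% to 14.5%.

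The direction depends on the assumption that the excluded subjects have the event. If the one excluded subject did not have an event seen in one other subject, the table would read 1/35 = 2.9% instead of 1/36 = 2.8%.

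**What does not move.** The planned 33 evaluable subjects can be reproduced without reference to the Safety set. A paired equivalence calculation on the log scale, with CV 31%, limits 0.80 to 1.25, a 90% interval and an assumed true ratio of 1, gives power 0.8006 at n = 33 and 0.7837 at n = 32.

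**The case against.** A reader might infer that the excluded subject's events vanish from the report. The text does not support that. Section 16.5.3 promises an overview and listing of all AEs without restricting either to an analysis set, so the event may still appear, and Section 9.8.2 requires the reason for discontinuation to be recorded. What remains is a disagreement between Sections 16.2.1 and 16.5.3 over the population behind the incidences.

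A reader might also infer that anyone who removes a pouch early is excluded. That does not follow either. Section 11.3.1 fixes the collection time for planned use but does not say that a pouch removed early is discarded, and Section 16.2.1 does not ask for a valid 60-minute result. Such a pouch could be assayed and keep the subject in the set. A swallowed, lost or unassayable pouch is the clear case.

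The situation is also likely to be rare. Subjects are daily users of at least five pouches with a year or more of use (Section 9.4), dosing is supervised (Section 10.6), and the effects reported so far are described as mild (Section 6.3). These facts limit the probability but do not repair the definition.

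Nor is 36 a fixed denominator, because Section 9.8.3 allows replacement. If one such subject were replaced, 37 would have been dosed and the Safety set could still hold 36: 0/36 against 1/37 = 2.7%.

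Deferring to the SAP does not answer the point. The protocol fixes the Safety set; a SAP that follows it carries the condition forward, and one that departs from it contradicts the protocol.

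**Conclusion.** The definition is wrong as written: membership of the Safety set depends on efficacy data, contrary to the protocol's own exposure-based definition and collection of AEs. The consequence is conditional. If at least one dosed subject yields no pouch result at all, AE incidences could be understated by at most k/36, which is 2.8% to 8.3% for an assumed 1 to 3 such subjects, all having the event. If there is no such subject, the FAS and the set of all dosed subjects coincide and nothing changes.

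The conclusion rests on reading efficacy data as pouch results, the only natural reading given the endpoints. If AEs counted as efficacy data, the condition would exclude none of these subjects and could be dropped without loss.

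A reader might treat this as a flaw that threatens the trial. The documents do not support that: the equivalence analysis, the sample size, AE collection and expedited reporting of serious events do not depend on the Safety set. It should be fixed before database lock.

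**What to change.** In Section 16.2:

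- Define a separate Safety analysis set: all subjects who received at least one dose of investigational product, whether or not any pouch data exist.
- Delete the sentence that makes the FAS the Safety set.
- Keep the efficacy-data condition for the FAS only.

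In Section 16.5.3, state that the AE summaries use the Safety set.

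The cost is a wording change, made by a written, numbered amendment under Section 13.5, with the SAP worded to match. No new data are needed, and sample size, power and significance level stay as they are.

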9.3 Number of subjects

36 subjects will be included in the study to achieve 33 fully evaluable subjects. It is estimated that approximately 56 subjects will be screened.

For replacements of subjects who discontinue from the study, see Section 9.8.

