9.10 Blinding

This is an open-label study, i.e. the Investigator, study staff and subjects will know the type of treatment to be received.

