14.5 Study time table and end of study

The study is expected to start in Q3 2020 and to be completed by Q4 2020.

A subject is considered to have completed the study if he/she has completed all visits in the study including the end-of-study telephone call (Visit 4).

The end of the clinical part of the study is defined as the last visit of the last subject participating in the study.

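### Per-protocol membership depends on completing the whole study, including the follow-up call, so valid A/B pouch pairs can drop out of the per-protocol equivalence comparison

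*Protocol*

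**What the plan says.** Section 16.2.2 of the protocol defines the PPS per subject. Members must be randomized and must have "completed the study without any major protocol deviations that are judged to compromise the analysis of the data". Section 14.5 gives the only definition of completion: a subject has completed the study on having "completed all visits in the study including the end-of-study telephone call (Visit 4").

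Section 9.9 places A (Wintergreen (1), nicotine extraction) and B (Smooth) at the start of the two treatment visits, one at each. The remaining doses of each visit follow. Table 8-1 puts Visit 4, a phone call, 5 days (-3/+3) after the last dose, and no pouch is collected then.

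On numbers, Section 9.3 states that "36 subjects will be included in the study to achieve 33 fully evaluable subjects", and Section 9.8.3 lets the sponsor replace prematurely withdrawn subjects at its discretion.

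On the timing of deviation grading, Section 16.2.2 says "All protocol violations will be judged as major or minor prior to database lock". Section 15.7 gives the order of events: "When all data have been entered and discrepancies solved, clean file will be declared, the database will be locked and the data will be analyzed". Section 11.3.1 says "Pouches for extraction of nicotine and flavor compounds will be analyzed by Swedish Match and Eurofins Food & Feed Testing Sweden", and Section 9.10 confirms the study is open-label.

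**The concern.** The two definitions read together make PPS membership depend on events after both primary pouches have been collected. Stopping partway through Visit 3, or not answering the follow-up call, says nothing about whether the A and B pouches were used and assayed properly. The words about compromising the analysis qualify the deviations; they do not soften the separate completion requirement.

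In an equivalence trial the per-protocol comparison is usually read beside the full-set result. Discarding sound pairs makes that comparison less precise, and the planned margin over the required number is modest.

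A second, weaker issue concerns timing. Grading has to precede database lock, but nothing requires it to precede receipt of the assay results. With no blinding and the manufacturer sharing the assay, the text does not rule out grading by someone who already knows the extraction values.

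**Working it through.** **Who is excluded.** Take a subject with valid A and B pouches and no major deviation.

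| Later event | A/B pair valid? | Completed under 14.5? | In PPS? | In FAS? |
|---|---|---|---|---|
| All doses and call done | yes | yes | yes | yes |
| Call missed | yes | no | no | yes |
| Stops after first dose of Visit 3 | yes | no | no | yes |

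The FAS column follows from Section 16.2.1, which asks only for randomization, one dose and one post-baseline efficacy assessment.

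**Reproducing the planned number.** Inputs from Section 16.2: CV 31%, 80% power, 90% confidence interval, limits 0.80 to 1.25. Assumptions, because the protocol does not state them: true ratio 1.00, 31% read as the within-subject CV, and a paired log-scale analysis with n - 1 degrees of freedom.

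- Log-scale SD = sqrt(ln(1 + 0.31²)) = sqrt(ln 1.0961) = 0.303.
- SD of the within-subject difference = 0.303 × sqrt(2) = 0.428.
- Standard error = 0.428 / sqrt(n); equivalence limits ln 0.80 = -0.223 and ln 1.25 = +0.223.
- Power = probability that both one-sided 5% t-tests reject, integrated over the distribution of the estimated SD.

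The smallest n with at least 80% power is 33 (power 80.06%), which matches the protocol.

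**Sensitivity to lost pairs under the same assumptions.**

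| Evaluable A/B pairs | Power, ratio 1.00 | Power, ratio 0.95 |
|---|---|---|
| 36 | 84.4% | 74.6% |
| 34 | 81.6% | 71.9% |
| 33 | 80.1% | 70.4% |
| 32 | 78.4% | 68.8% |
| 31 | 76.6% | 67.2% |
| 30 | 74.6% | 65.4% |

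At ratio 1.00, going from 34 to 33 pairs costs 81.62 - 80.06 = 1.6 points, and from 33 to 32 costs 80.06 - 78.37 = 1.7 points. Without replacement, the margin is 36 - 33 = 3 subjects, and a fourth lost pair (36 - 4 = 32) takes power just under 80%.

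If 31% is instead the total CV and the within-subject correlation is 0.5, 18 pairs suffice (power 82.4%), and a few lost pairs would not matter.

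**Grading.** Section 15.7 puts the statistical analysis after lock, but lock itself comes only once all data are entered. Section 15.5 notes that "External data consists of data that are not recorded in the eCRF" and sets no release date for them. No section says who grades deviations or what they may have seen.

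**The case against.** A reader might infer that these subjects are thrown out of the primary analysis. The protocol does not say so. Section 16.4.1 names no analysis set for the equivalence test, the FAS keeps every subject at issue, and Section 16 leaves technical detail to an SAP that is not shown. This stands: the loss arises only where the PPS is used for the claim or must agree with it.

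A reader might also take the three spare subjects as the whole margin and suppose that several missed calls would push power well below target. The documents give no rate of missed calls or late withdrawals. The call has a window of three days either side, the study is short, and Section 9.8.3 allows replacement. So the power table shows sensitivity and is not a forecast. Replacement is discretionary, however, and adds a new pair without restoring the valid one set aside.

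On grading, a reader might infer that exclusions will be decided with the results in view. That is not shown. Grading before lock is conventional, the contract research organization performs the analyses (Section 16), and release controls may sit in the SAP or the Data Management Plan. What remains is an opening in the text, not a demonstrated fault.

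Finally, one PPS serves the whole study, and completion of later doses is relevant to the secondary comparisons among other products. That justifies a requirement for those doses in those comparisons. It does not justify one for A versus B, and it gives no reason to require the telephone call.

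**Conclusion.** The point holds in a limited form. As written, the PPS excludes subjects whose A and B pouches are both valid, for reasons that do not bear on the validity of those data. This follows from Sections 16.2.2 and 14.5 taken together and needs no assumption.

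The consequence is conditional on the PPS having a role in the equivalence conclusion, and it is probably small. The cost of 1.6 to 1.7 points of power per lost pair rests on a true ratio of 1.00 and on 31% being the within-subject CV; it would be negligible if the 31% already includes between-subject variation at a moderate correlation.

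The documents support neither a claim that the primary test will be underpowered nor one that exclusions will be outcome-driven. Fixing the time of grading is worth doing as an inexpensive precaution. The change to the set is worth making because the rule has no benefit for the primary comparison.

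**What to change.** In Section 16.2.2, define the PPS for the A versus B comparison as all randomized subjects with valid A and B pouches and no major deviation affecting either administration, without requiring Visit 4 or the later doses. Deviations that plausibly matter can be named from the protocol's own requirements: use time outside 60 ± 1 minutes (Section 11.3.1), eating or drinking within the restricted period, a breach of nicotine abstinence, or a lost or damaged pouch. Secondary product comparisons may keep a requirement for the doses they use.

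In the same section, require the major/minor grading to be final before pouch assay results are released to those who grade, in place of only before database lock.

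The cost is a few sentences in the protocol, carried into the SAP, and somewhat earlier grading. No subjects, visits or assays are added, and the planned 33 and 36 are unchanged.
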